#### 2.2. Endpoints

#### 2.2.1. **Primary Endpoints**

The primary safety endpoints for this study are as follows:

- incidence and severity of AEs
- incidence of laboratory abnormalities, based on haematology, clinical chemistry, coagulation, and urinalysis test results
- vital signs measurements
- 12-lead ECG parameters
- telemetry
- neurological examinations
- Columbia-Suicide Severity Rating Scale (C-SSRS)
- physical examinations.

#### 2.2.2. Secondary Endpoints

For Part A, the single-ascending dose and food (fed versus fasted dietary status at dosing), PK outcome endpoints of AM1476 are as follows:

- area under the plasma concentration-time curve from time zero to infinity (AUC0-∞)
- area under the plasma concentration-time curve from time zero to the time of the last quantifiable concentration (AUC0-tlast)
- maximum observed plasma concentration (Cmax)
- time of the maximum observed plasma concentration (tmax)
- apparent plasma terminal elimination half-life  $(t_{\frac{1}{2}})$

- apparent total plasma clearance (CL/F)
- apparent volume of distribution (Vz/F)
- renal clearance (CLR)
- amount of drug excreted in the urine (Ae)
- percentage of drug excreted in the urine (Fe).

For Part B, the multiple-ascending dose PK outcome endpoints of AM1476 are as follows:

- area under the plasma concentration-time curve over a dosing interval  $(AUC_{0-\tau})$
- $AUC_{0-\infty}$  (Day 1 only)
- Cmax
- minimum observed plasma concentration (Cmin)
- tmax
- t/2
- CL/F
- Vz/F
- observed accumulation ratio based on AUC0-τ (RAAUC0-τ)
- observed accumulation ratio based on Cmax (RACmax)
- CLR
- Ae
- Fe.

Other PK parameters may also be reported.

#### 3. INVESTIGATIONAL PLAN

#### 3.1. Overall Study Design and Plan

This will be a double-blind, randomised, placebo-controlled, single- and multiple-oral dose study conducted in 2 parts.

#### **3.1.1.** Part A

Part A will comprise a single-ascending dose, sequential-group design incorporating a single-group, 2-period crossover arm incorporating a food-effect evaluation. Overall, 48 subjects will be studied in 6 groups (Groups A1 to A6), with each group consisting of 8 subjects.

Potential subjects will be screened to assess their eligibility to enter the study within 28 days prior to the first dose administration (within 35 days for Group A1). Each subject will participate in 1 treatment period only, except for those participating in a food-effect

evaluation, where each subject will participate in 2 treatment periods separated by a minimum of 6 days.

Subjects will reside at the Clinical Research Unit (CRU) from Day -1 (the day before dosing) to Day 3 of each treatment period, as applicable. All subjects will return for a Follow-up visit 7 to 10 days after their final dose.

Based on the ongoing review of the safety, tolerability, and PK results, additional non-residential visits may be required. The number of additional visits per subject will not exceed 3 per period and will not extend beyond 28 days after each final dosing occasion.

In each of Groups A1 to A6, 6 subjects will receive AM1476 and 2 subjects will receive placebo.

#### Groups A1, A2, and A4 to A6

It is planned for each subject in Groups A1, A2, and A4 to A6 to receive only a single dose of AM1476 or placebo during the study. Doses will be administered in the fasted state in accordance with a randomisation schedule on the morning of Day 1.

#### Group A3

It is planned for each subject in Group A3 to have the same treatment in both treatment period such that each subject will receive 2 single doses of AM1476 or placebo during the study. On Day 1 in Treatment Period 1, doses will be administered in the fasted state in accordance with a randomisation schedule. On Day 1 in Treatment Period 2, doses will be given 30 minutes after starting a standard high-fat breakfast. Although a food-effect evaluation is planned to occur in Group A3, this may be subject to change depending upon ongoing review of the PK data.

#### Additional Groups (Groups A7 to A9)

If it is decided to enrol additional groups (Section 3.3), the effect of food on the PK of AM1476 may further be evaluated as described for Group A3. However, fasting requirements, meal compositions, and timing of doses will be determined following review of the available PK data.

[figure not shown]
#### **Sentinel Dosing**

All groups in Part A will be divided into 2 cohorts, with each cohort being dosed at least 24 hours apart. The first cohort will comprise 2 subjects, with 1 subject receiving AM1476 and 1 subject receiving placebo. The second cohort will comprise 6 subjects, with 5 subjects receiving AM1476 and 1 subject receiving placebo. For groups participating in a food-effect evaluation, sentinel dosing will only be utilised in Treatment Period 1 when AM1476 or placebo are administered in the fasted state. Dosing of subjects in the second cohort will not continue if any of the dose escalation stopping criteria (Section 3.7) are met by the sentinel subjects (first cohort).

The total duration of study participation for each subject (from Screening through Follow-up visit) is anticipated to be approximately 6 weeks for subjects not participating in the food-effect evaluation (approximately 7 weeks for Group A1) and approximately 7 weeks for those participating in the food-effect evaluation.

[figure not shown]
An overview of the study design is shown in Figure 1 and Figure 2, and the planned dose levels in Figure 3. A Schedule of Assessments is presented in Appendix 6.

#### Figure 1: Study Schematic (Part A) for Groups A1, A2, and A4 to A6

[figure not shown]
Abbreviations: CRU = Clinical Research Unit; N = number of subjects. Note: Group A1: Screening period from Day -35 to Day -2 (approximately 5 weeks)

#### Figure 2: Study Schematic (Part A) for Food-effect Evaluation(s)

Abbreviations: CRU = Clinical Research Unit; N = number of subjects.

# Figure 3: Planned Dose Levels (Part A)

Abbreviations: N = number of subjects; PK = pharmacokinetic(s); TBD = to be determined.

NOTE: dose levels may be adjusted based on the ongoing review of the safety, tolerability, and PK data. Doses will be administered in an escalating manner following satisfactory review by the Sponsor and Investigator of the safety and tolerability data (up to 48 hours post-final dose) and plasma PK data (up to 24 hours post-final dose [ie, Day 1 in Part A]) from the lower dose levels.

Although the food-effect evaluation is planned to occur in Group A3, this may be subject to change depending upon ongoing review of the PK data.

#### 3.1.2. Part B

Part B will comprise a multiple-ascending dose, sequential-group design. Overall, it is planned for 24 subjects to be studied in 3 groups (Groups B1 to B3), with each group

consisting of 8 subjects. Part B may start following review of the safety and tolerability and PK data for Group A4, at a dose equal or less than given in Groups A1 to A4, provided the predicted exposure is not expected to exceed an exposure already shown to be safe and well tolerated. The dose level cannot be equal to a dose level from Part A if that dose met any of the dose escalation stopping rules.

Potential subjects will be screened to assess their eligibility to enter the study within 28 days prior to the first dose administration. Each subject will participate in 1 treatment period only and reside at the CRU from Day -1 until the morning of Day 12. All subjects will return for a Follow-up visit 7 to 10 days after their final dose.

[figure not shown]
Based on the ongoing review of available safety, tolerability, and PK data, up to 3 additional non-residential visits may be required. The number of additional visits per subject will not exceed 3 and will not extend beyond 28 days after each final dosing occasion.

In each of Groups B1 to B3, 6 subjects will receive AM1476 and 2 subjects will receive placebo. The dietary state for dosing in Part B will be subject to review of the PK data from the fed/fasted comparison in Part A. For all subjects, dosing is planned to be QD on Days 1 to 10, inclusive. However, the dietary state (including fasting requirement and meal compositions), dosing duration, and dosing frequency may be changed following review of safety, tolerability, and PK data from Part A or earlier groups in Part B (Section 3.4). The dose regimen will comprise no less than once every 2 days and will not exceed BID dosing. The predicted total daily exposure at the selected dose administered will not exceed an exposure shown to be safe and well-tolerated in Part A. The dosing duration will comprise no fewer than 7 consecutive days and will not exceed 28 consecutive days. There will be a minimum of 6 days between dose escalations for each group.

The total duration of study participation for each subject (from Screening through Follow-up visit) is anticipated to be approximately 7 weeks.

An overview of the study design is shown in Figure 4, and the planned dose levels in Figure 5. A Schedule of Assessments is presented in Appendix 7.

[figure not shown]
#### Figure 4: Study Schematic (Part B)

Abbreviations: BID = twice daily; CRU = Clinical Research Unit; N = number of subjects; QD = once daily.

a. Dosing is planned to be QD on Days 1 to 10, inclusive. The dosing regimen in Part B may be changed following review of data from groups in Part A or earlier groups in Part B. The dose regimen will comprise no less than once every 2 days and will not exceed BID dosing. The dosing duration will comprise no fewer than 7 consecutive days and will not exceed 28 consecutive days.

#### Figure 5: Planned Dose Levels (Part B)

Abbreviations: BID = twice daily; N = number of subjects; QD = once daily; TBD = to be determined. NOTE: doses will be administered in an escalating manner following satisfactory review by the Sponsor and Investigator of the safety and tolerability data (up to 48 hours post-final dose) and plasma PK data (up to 24 hours post-final dose [ie, Day 1 in Part A and Day 10 in Part B]) from Part A or earlier groups in Part B.

a. Dosing is planned to be QD on Days 1 to 10, inclusive. The dosing regimen in Part B may be changed following review of data from groups in Part A or earlier groups in Part B and will not exceed BID dosing.

#### **3.2.** Study Start and End of Study Definitions

The start of the study is defined as the date the first subject signs an Informed Consent Form (ICF). The point of enrolment occurs at the time of subject number allocation. The end of the study is defined as the date of the last subject's last assessment (scheduled or unscheduled).

#### **3.3.** Additional Groups

Following review of the safety, tolerability, and PK data, additional dose groups (where systemic exposure is not expected to exceed that stated in the dose escalation stopping criteria [Section 3.7]) may be added to the study. There will be no further dose escalation in these additional groups if dose escalation stopping criteria have been met and a dose level cannot be repeated if it previously met a stopping criterion. Up to 3 further groups of 8 subjects (6 active:2 placebo) may be included in each of Parts A and B. The requirement for additional groups will be agreed with the Sponsor and documented in the Trial Master File (TMF).

#### 3.4. Discussion of Study Design, Including the Choice of Control Groups

For both parts of the study, a sequential-group, ascending-dose design has been chosen for safety reasons as AM1476 is in the early stages of clinical development, with Part A of the study being the first time it will be administered to humans. Oral doses have been chosen for both parts of the study, as this is the intended clinical route of administration. A 2-period crossover design has been chosen for the food-effect arm, as this gives a within-subject assessment of the influence of food on the PK of AM1476 and so increases the power of the study for the given number of subjects.

It is the intent of Part B to dose subjects such that steady-state plasma levels of AM1476 are achieved and maintained for several days. Based on the available non-clinical data, it is expected that this will be achieved following 10 days of QD dosing; however, a full review of all the safety, tolerability, and PK data from Part A will be performed to confirm the dose regimen for Part B. If the  $t_{1/2}$  of AM1476 is shorter than predicted by the non-clinical data, BID dosing over 7 days may be appropriate. If the  $t_{1/2}$  of AM1476 is longer than predicted by the non-clinical data, QD dosing may be more appropriate over 28 days (as steady-state will take longer to achieve). The dose regimen will comprise no less than once every 2 days and will not exceed BID dosing. The dosing duration will comprise no fewer than 7 consecutive days and will not exceed 28 consecutive days of dosing.

Details of the dosing regimen and duration used for Part B of the study will be documented in the TMF.

Based upon the non-clinical data, the duration of each treatment period is considered adequate to achieve the study objectives. Where applicable, an interval of at least 6 days between treatment periods in the food-effect arm is considered adequate to prevent carryover of AM1476.

This study will be double-blind and placebo-controlled in order to avoid bias in the collection and evaluation of data during its conduct. Placebo has been chosen as the control treatment to assess whether any observed effects are treatment-related or simply reflect the study conditions.

Conducting the study in healthy subjects mitigates the potential confounding effects of the disease state and concomitant medications.

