# 5.3. Randomisation

The randomisation code will be produced by the statistics department at Covance using a computer-generated pseudo-random permutation procedure.

In Part A, 6 subjects per group will be randomly assigned to receive AM1476 and 2 subjects per group will be randomly assigned to receive placebo, and subjects in Group A3 will receive the same treatment in Treatment Periods 1 and 2. For all groups in Part A, sentinel dosing will occur whereby 2 subjects (1 active and 1 placebo) will be dosed on 1 day and, providing no safety concerns arise, the remaining 6 subjects (5 active and 1 placebo) will be dosed after at least 24 hours.

In Part B, 6 subjects will be randomly assigned to receive AM1476 and 2 subjects per group will be randomly assigned to receive placebo.

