6. STUDY TREATMENTS

The study treatment names and ordering to be used in the TFLs for Part A are presented in Table 1 and for Part B in Table 3. The study treatment sequence names and ordering to be used in listings for food-effect group(s) in Part A only are presented in Table 2.

Group	Study Treatment	Order in TFLs
A1 to A9	Placebo ^a	1
A1	1 mg AM1476 (Fasted)	2
A2	XX mg AM1476 (Fasted)	3
A3	XX mg AM1476 (Fasted)	4
	XX mg AM1476 (Fed)	5
A4	XX mg AM1476 (Fasted)	6
A5	XX mg AM1476 (Fasted)	7
A6	XX mg AM1476 (Fasted)	8
A7 ^b	XX mg AM1476 (Fasted)	9
	XX mg AM1476 (Fed) ^c	10
A8 ^b	XX mg AM1476 (Fasted)	11
	XX mg AM1476 (Fed) ^c	12
A9 ^b	XX mg AM1476 (Fasted)	13
	XX mg AM1476 (Fed) ^c	14

Table 1: Presentation of Study Treatments in TFLs (Part A)

a. Placebo will be pooled across all groups and fasting conditions

b. Optional group, to be included if required

c. Optional group may or may not include food-effect evaluation

Table 2:Presentation of Study Treatment Sequences in Listings (Food-effect
Group(s) in Part A Only)

Group	roup Study Treatment Sequence	
A3	Placebo (Fasted) / Placebo (Fed)	1
	XX mg AM1476 (Fasted) / XX mg AM1476 (Fed)	2
A7 ^{a,b}	Placebo (Fasted) / Placebo (Fed)	3
	XX mg AM1476 (Fasted) / XX mg AM1476 (Fed)	4
A8 ^{a,b}	Placebo (Fasted) / Placebo (Fed)	5
	XX mg AM1476 (Fasted) / XX mg AM1476 (Fed)	6
A9 ^{a,b}	Placebo (Fasted) / Placebo (Fed)	7
	XX mg AM1476 (Fasted) / XX mg AM1476 (Fed)	8

a. Optional group, to be included if required

b. Optional group may or may not include food-effect evaluation

Group	Study Treatment	Order in TFLs
B1 to B6	Placebo ^a	1
B1	XX mg AM1476 (QD) (Fasted)	2
B2	XX mg AM1476 (QD) (Fasted)	3
B3	XX mg AM1476 (QD) (Fasted)	4
B4 ^b	XX mg AM1476 (QD) (Fasted)	5
B5 ^b	XX mg AM1476 (QD) (Fasted)	6
B6 ^b	XX mg AM1476 (QD) (Fasted)	7

Table 3:	Presentation of Study Treatments in TFLs (Part B)
----------	---------------------------------------------------

Abbreviations: QD = once daily

a. Placebo will be pooled across all groups

b. Optional group, to be included if required

All TFLs will be based on actual treatments (eg, if subject was assigned to receive placebo but was wrongfully dosed with active treatment they would be summarised and listed under active treatment).

All dose levels described above are the potential dose levels, and therefore are subject to change. The TFLs will reflect the dose levels utilised in the study, and these will be displayed in increasing order.

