8.5.1.5. Treatment of Outliers in Pharmacokinetic Analysis

If a value is considered to be anomalous due to being inconsistent with the expected PK profile, it may be appropriate to exclude this point from the PK analysis. However, the exclusion of data must have strong justification and will be documented in CSR.

Any quantifiable predose concentration value on the first dosing day of all parts of the study (profile day 1) will be considered anomalous and set to missing for the PK analysis. This will be set to 0 by default in Phoenix WinNonlin.

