8.5.3.2. Food-effect Assessment

A statistical analysis will be conducted to investigate the food-effect on the treatment by comparing AM1476 (fed) treatment to AM1476 (fasted) at the same dose level.

The hypothesis testing will be 2-sided and carried out on both 0.05 and 0.1 significance levels.

The ln-transformed⁵ AUC_{0-tlast}, AUC_{0- ∞}, and C_{max} on profile day 1 for food-effect group(s) in Part A (only for plasma AM1476) will be analysed using a mixed model.⁷ The model will include actual treatment as fixed effect and subject as a random effect.

For each PK parameter separately, the least squares mean (LSM) for each treatment, difference in LSMs between the fed and fasted treatments, and corresponding 90% and 95% CIs will be calculated; these values will then be back-transformed to give the GLSM, ratio of GLSMs, and corresponding 90% and 95% CIs.

Additionally, the pooled estimate (across treatments) of the within-subject CV will be calculated, and residual plots will be produced to assess the adequacy of the model(s) fitted.

Examples of the SAS code that will be used are as follows:

Mixed Model Analysis

```
proc mixed data = <data in>;
by parcatln parcatl pkday paramn param;
class trtan usubjid;
model lpk = trtan / cl residual ddfm = kr2;
lsmeans trtan / cl pdiff = control('1') alpha = 0.1;
lsmeans trtan / cl pdiff = control('1') alpha = 0.05;
random intercept / subject = usubjid;
ods output lsmeans = <data out>;
ods output diffs = <data out>;
ods output covparms = <data out>;
run;
```

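### Group A3 tests food in one order only (fasted, then fed), so the fed/fasted ratio is food times period, and the SAP's predose rule would set aside the direct evidence of carryover

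*Protocol*

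**What the plan says.** Protocol 3.4 explains the food-effect arm this way: "A 2-period crossover design has been chosen for the food-effect arm". Its reason is the within-subject comparison and the power this gives. It relies on a washout of at least 6 days to prevent carryover and does not mention period effects. The synopsis, Protocol 3.1.1 and SAP 4.1 also call the arm a crossover.

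The order is fixed. For Period 1 of Group A3: "On Day 1 in Treatment Period 1, doses will be administered in the fasted state in accordance with a randomisation schedule". For Period 2: "On Day 1 in Treatment Period 2, doses will be given 30 minutes after starting a standard high-fat breakfast". Protocol 5.3 randomises active against placebo and adds that "subjects in Group A3 will receive the same treatment in Treatment Periods 1 and 2". SAP Table 2 lists a single active sequence, fasted then fed, for Group A3 and for optional Groups A7 to A9. For those optional groups, Protocol 3.1.1 says "the effect of food on the PK of AM1476 may further be evaluated as described for Group A3", with fasting, meals and dose timing left open until PK review.

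On the analysis, SAP 8.5.3.2 says: "The model will include actual treatment as fixed effect and subject as a random effect". It reports the fed/fasted ratio with 90% and 95% CIs and two-sided tests at 0.05 and 0.1.

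On predose samples, SAP 8.5.1.5 covers "Any quantifiable predose concentration value on the first dosing day of all parts of the study", which it labels profile day 1. It calls such a value anomalous and sets it to missing for the PK analysis, after which the software uses 0.

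**The concern.** A crossover with both orders lets period be estimated and removed from the treatment contrast. With one order, whatever differs between Period 1 and Period 2 goes into the food ratio, and the analysis cannot show that it has. The plan reports the result as a food effect without stating the assumption this needs.

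The food effect is a secondary objective, and the fed/fasted PK data inform the dietary state reviewed for Part B. This is also a first-in-human study. The washout rests on non-clinical data, and Protocol 3.4 itself allows that the half-life may prove longer than predicted. The Period 2 predose sample is the plan's direct check on that washout, and SAP 8.5.1.5 would take a quantifiable result out of the analysis as an anomaly.

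**Working it through.** The documents give no sample size, variance or effect size for the food comparison, so there is no stated figure to reproduce.

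**Inputs.**
- Six active subjects in Group A3, two periods (Protocol 3.1.1), so 12 observations per parameter.
- All fasted then fed (Protocol 3.1.1; SAP Table 2).
- Model terms: treatment and subject (Protocol 8.3; SAP 8.5.3.2).
- Placebo samples are not assayed (Protocol 7.1.1), and the other planned Part A groups have one period, so no other data inform period.
- Assumed, not in the documents: period ratios 0.80 to 1.25, and within-subject CV 15% to 40%.

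**Step 1: what the ratio estimates.** Write ln(y) = subject + φ·fed + π·(period 2). For every Group A3 subject, fed = 0 in Period 1 and 1 in Period 2. The within-subject difference therefore has expectation φ + π on the log scale. Back-transformed, the estimate is food ratio × period ratio. Carryover occurs only in Period 2 and enters the same sum.

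**Step 2: can period be separated?** I checked the rank of the design matrix.
- As written, subject + food: 7 columns, rank 7, 12 − 7 = 5 residual df.
- As written, with period added: 8 columns, rank still 7, because the fed and Period 2 indicators are identical.
- For comparison only, three subjects in each order with period: 8 columns, rank 8, 4 residual df, and the food ratio is recovered exactly. This shows that the single order causes the aliasing; it does not propose a dosing order.

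**Step 3: size under assumed period ratios.**

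| True food ratio | Assumed period ratio | Expected reported ratio |
|---|---|---|
| 1.00 | 0.80 | 0.80 |
| 1.00 | 0.90 | 0.90 |
| 1.00 | 1.10 | 1.10 |
| 1.00 | 1.25 | 1.25 |
| 1.25 | 0.80 | 1.00 |
| 1.25 | 0.90 | 1.125 |
| 1.25 | 1.10 | 1.375 |
| 1.25 | 1.25 | 1.5625 |

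**Step 4: set against precision.** The 90% CI multiplier is exp(t(0.95, 5) × σw × √(2/6)), with σw = √ln(1 + CV²). At CV 20%, σw = 0.198, SE = 0.198 × √(2/6) = 0.114 and half-width = 2.015 × 0.114 = 0.230. An estimate of 1 then has limits 0.79 to 1.26. The multiplier is 1.190 at CV 15%, 1.407 at 30% and 1.565 at 40%. A 10% upward shift is ln(1.10) = 0.095, or 0.095/0.230 = 0.41 of the half-width at CV 20%. The interval reflects sampling error only and makes no allowance for the shift.

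**Step 5: does the predose rule reach Period 2?** Appendix 6 applies the same schedule, including the predose sample, to Period 2 of Group A3. SAP 8.5.3.2 analyses both the fed and the fasted data under the label profile day 1. SAP 8.5.1.5 defines its rule by that same label, so on the SAP's own usage it covers Period 2.

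**Step 6: what setting the value to 0 does.** The first postdose sample is at 0.25 h. Under the linear rule for rising concentrations, replacing a predose value Cpre by 0 removes 0.25 × Cpre/2 = 0.125 × Cpre from the AUC. Later concentrations are untouched, so any residual drug in them stays in the Period 2 AUC and Cmax. The rule removes the marker of carryover from the analysis but leaves nearly all of its effect.

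**The case against.** The order is openly stated throughout both documents, and the reason given in Protocol 3.4 is true: each subject is their own control, and that does raise power. The protocol nowhere claims period balance. A reader might infer that the comparison is invalid or its rationale false; the documents do not support that.

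A reader might also infer that the ratio is biased. Nothing in the documents shows a period effect. Dosing is supervised, meals on intensive PK days are standardised, and the period ratios and CVs above are assumptions. At CV 20%, imprecision outweighs a 10% shift, and SAP 8.1 already urges caution on sample-size grounds.

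It would be too strong to say that the predose rule hides carryover. SAP 8.5.2 lists all concentrations, and SAP 8.5.1.5 requires exclusions to be documented in the study report. One could also read the rule's reference to the first dosing day as Period 1 only, but the profile day 1 label points the other way, and the text should settle it.

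Nor does the food-effect CI decide the Part B diet. Protocol 3.1.2 leaves that to review of the PK data and allows later change.

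Finally, a reader might want the order randomised in Groups A7 to A9. Protocol 3.1.1 applies sentinel dosing to all Part A groups and, in food-effect groups, confines it to a fasted Period 1. Randomised order would conflict with that.

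All of this stands. It does not answer the missing assumption, the label, or the treatment of a Period 2 predose value.

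**Conclusion.** The point holds in a limited form. Group A3 is a fixed-sequence paired comparison. Food and period are fully aliased, so the ratio carries any period effect at full size and no term added to the model can remove it. This follows from the design and needs no numerical assumption; only the illustrative sizes do. The documents give no evidence either way on whether a period effect exists, and they do not state that its absence is assumed.

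Carryover differs from other period effects because the scheduled Period 2 predose sample can reveal it. SAP 8.5.1.5 as worded would classify that evidence as an anomaly and drop it from the PK analysis, although it would remain in the listings. A Period 2 predose value below the assay limit would support the washout claim but would say nothing about other period effects.

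**What to change.** - **SAP 8.5.1.5:** limit the set-to-missing/0 rule to the first dose a subject receives. Keep Period 2 predose values in the PK analysis and report them as carryover next to the food-effect ratio. Make clear that they are not excluded from summaries as anomalous under SAP 8.5.2.
- **Synopsis, Protocol 3.1.1 and 3.4, SAP 4.1:** replace *crossover* with *fixed-sequence (fasted then fed)*. The within-subject rationale can stay.
- **SAP 8.5.3.2:** state that the ratio is food times period and is read as a food effect on the assumption of no period effect. Carry this into the study report as a limitation.

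No change to dosing order is proposed for Group A3 or for Groups A7 to A9. Subjects, visits, samples and the model stay the same. The cost is a few lines of text, one small additional display, and a slightly more qualified food-effect conclusion.
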